PROTOCOL COVER PAGE

PROTOCOL NAME

Can brief exposure to hyperoxia improve function after chronic spinal cord injury?

PROTOCOL IDENTIFYING NUMBER

Pro00061817

PROTOCOL AMENDMENT VERSION

Version 13

PROTOCOL AMENDMENT DATE

October 1, 2021

GENERAL INFORMATION

Name and address of the sponsor and monitor of the study

University of Alberta, Edmonton, AB.

Name and address of the person authorized to sign the protocol and amendments

[name] [name], [name], University of Alberta

Name, title, address and telephone number(s) of the medical expert for the trial

[name], Associate Professor, Pulmonary Medicine, [name],
University of Alberta
[contact]

Name and title of the investigator(s) and sub-investigators responsible for the trial with address and phone number(s)

[name], Professor, [name], University of Alberta. [contact]
[name], Professor, [name], University of Alberta. [contact]
[name], Professor, [name], University of Alberta. [contact]
[name], Associate Professor, [name], University of Alberta. Tel: [name]
[name], Professor, [name], University of Alberta. [contact]

Name, title and address of qualified physician who is responsible for trial-site related medical decisions

[name], Associate Professor, Pulmonary Medicine, [name],
University of Alberta
[contact]

Trial site location and contact

Location: [name], University of Alberta, Edmonton, AB
[contact]
Physical therapist: [name]

Study Summary

Title	Can brief exposure to hyperoxia improve function after chronic spinal cord injury?
Short Title	N/A
Protocol Number	Pro00061817, Version 13
Phase	Proof-of-principle study
Methodology	Prospective, double-blind, randomized crossover design
Study Duration	Projected end date March 31, 2026
Study Center(s)	Single centre
Objectives	Determine if breathing an increased proportion of oxygen above the concentration in normal room air results in changes in the sensory and motor function in people with severe spinal cord injury (SCI).
Number of Subjects	35 (25 with spinal cord injury, 10 uninjured controls)
Diagnosis and Main Inclusion Criteria	Chronic and subacute, traumatic spinal cord injury; uninjured healthy controls for ensuring experimental protocol without using oxygen

1.1 Investigational Agent

Pure oxygen (99%) from Praxair, Edmonton, DIN# 02014408, delivered through a face mask at a flow rate of 10 litres/min, for a period of 2 minutes. Reference (placebo) agent is compressed air from Praxair, DIN# 02014483, delivered in the same way.

1.2 Preclinical Data

An abstract from the preclinical trial in rodents is included below. This study details the mechanisms underlying chronic hypoxia in the spinal cord distal to a complete spinal cord transection in a rodent model, and how brief exposure to breathing high levels of oxygen modifies the motor behaviour of the rodent. Because there is no way to measure the oxygenation in the human spinal cord non-invasively, we wish to determine if brief exposure to pure oxygen in a human with severe spinal cord injury modifies the sensory and motor behaviour in a way similar to that in rodents. If so, it would suggest that the human spinal cord distal to a severe spinal cord injury is also chronically hypoxic, and interferes with sensory and motor function. Ways to restore oxygenation to the spinal cord could then be pursued in future studies.

Pericytes impair capillary blood flow and motor function after chronic spinal cord injury

Yaqing Li¹, Ana M. Lucas-Osma¹, Sophie Black¹, Mischa V. Bandet², Marilee J. Stephens¹, Romana Vavrek¹, Leo Sanelli¹, Keith K. Fenrich¹, Antonio Dinarzo³, Stella Dracheva³, Ian R. Winship², Karim Fouad¹ and David J. Bennett¹

¹Neuroscience and Mental Health Institute and Faculty of Rehabilitation Medicine, University of Alberta, Canada; ²Neuroscience and Mental Health Institute and Department of Psychiatry, University of Alberta, Canada; ³Department of Genetics and Genomic Sciences, Icahn School of Medicine at Mount Sinai, New York, NY, USA

Nature Medicine (2017) 23(6):733 doi:10.1038/nm.4331¹

ABSTRACT

Blood vessels in the CNS are controlled by neuronal activity, including widespread vessel constrictions (tone) induced by brainstem neurons that release the monoamines serotonin and noradrenaline, and local vessel dilation mediated by glutamatergic neuron activity. We examine how vessel tone adapts to the loss of these monoamines after spinal cord injury (SCI) in rats. We find that, months after SCI, the cord below the injury is in a chronic state of hypoxia, produced by a paradoxical excess activity in monoamine receptors (5-HT1), despite the absence of monoamines. These receptors activate pericytes that locally constrict capillaries, reducing blood flow to ischemic levels. The paradoxical receptor activity results from trace amines (tryptamine) produced by pericytes that ectopically express the enzyme aromatic-L-amino-acid-decarboxylase (AADC),

which synthesizes trace amines directly from dietary amino acids (tryptophan). However, blocking monoamine receptors or AADC, or briefly inhaling increased oxygen, produces long-term relief from hypoxia and improves locomotor function.

1.3 Risk/Benefits

Oxygen therapy with up to 100% oxygen for much longer than we propose to use (which is 2 mins) is used in the management of pulmonary conditions and emergency medicine (Vogelsinger et al 2017; Branson 2018; Brugniaux et al 2018), and is also used to enhance physical performance in athletics (Brugniaux et al 2018). Symptoms of oxygen toxicity does not start to develop in humans breathing pure oxygen at normobaric (i.e., 1 atmospheric pressure, which is our proposed condition) until after 4 - 24 hours of exposure (Klein 1990). People with chronic, spinal cord injury have been exposed to much longer duration of oxygen (up to 4 hours) with no adverse effects reported (Gui et al 2014).

If there is any sign of discomfort during an experiment suggestive of early stage oxygen toxicity, such as tracheal irritation, abnormal rise in blood pressure or other symptoms (Klein 1990), oxygen will be discontinued. [name] (co-investigator and medical expert on this trial) will be available by phone during all experiments with participants with spinal cord injury, and a licensed Physiotherapist (PT) will be present during these experiments.

If a participant has any signs of distress (related or unrelated to the study), the PT will evaluate the situation, and contact [name] for consultation, or arrange for transportation to the emergency department if warranted. The laboratory where all the experiments will take place is located in the Clinical Sciences Building at the University of Alberta. This Building is physically connected with the University of Alberta Hospital.

1.4 Dose Rationale

Oxygen is delivered in the same way as has been tested in rodents. The percentage of oxygen is also similar to that used in the animal study (Li et al 2017). The period of exposure is chosen to be slightly longer than that used in rodents (1 min in rodents vs 2 min in humans) to allow delivery of oxygen in a much larger organism, but still well below the time frame when complications have been reported (≥ 4 hours) (Klein 1990).

1.5 Trial Conduct

This study will be conducted in compliance with the protocol approved by the University of Alberta Health Research Ethics Board (HREB), and according to Good Clinical Practice (GCP) standards. No deviation from the protocol will be implemented without the prior review and approval of the HREB, except where it may be necessary to eliminate an immediate hazard to a research subject. In such case, the deviation will be reported to the HREB as soon as possible.

1.6 Population

Subacute or chronic (≥ 3 months post-injury), traumatic spinal cord injury. See inclusion and exclusion criteria (Sections 4.1 and 4.2, respectively, below).

A small number of uninjured participants will be included to test the experimental set-up using compressed air only. These participants will not be included in the testing of the experimental agents, but rather are used to ensure that the protocol runs smoothly prior to testing participants with spinal cord injury.

1.7 Literature

Ways to promote recovery from severe spinal cord injury has been extremely limited in humans. Individuals with spinal cord injury, diagnosed with ASIA Impairment Scale A and B, have historically tended not to improve a great deal over time, or even progressively decrease in function (Steeves et al 2011; Zariffa et al 2011; Aimetti et al 2019). Recently, epidural stimulators implanted over the spinal cord have resulted in some return of function in such individuals (Harkema et al 2011; Angeli et al 2014; Angeli et al 2018), but it requires surgical implantation of a stimulator, which comes with all the potential complications of such a procedure.

Recent work in rats with complete and incomplete spinal cord injuries (Li et al 2017) suggests that the spinal cord distal to the lesion site suffers from chronic hypoxia, resulting from excessive activity of monoamine receptors in pericytes, which surround capillaries and constrict blood flow. Brief (1 min) inhalation of pure oxygen in these rats reduces the hypoxia for ~ 20 min, resulting in improved motor and sensory function. We will test this idea in humans with chronic, severe, spinal cord injury.

2 Trial Objectives

Determine if breathing an increased proportion of oxygen above the concentration in normal room air results in changes in the sensory and motor function in people with sub-acute and chronic, severe spinal cord injury (SCI).

3 Trial Design

The scientific integrity of the trial and the credibility of the data from the trial depend substantially on the trial design. The trial design is as follows (shown in schematic form in Figure 1).

[figure not shown]

Figure 1. Crossover experimental design for participants with spinal cord injury. Participants will be randomized into Group 1 or Group 2. Group 1 will receive oxygen during Phase 1, and compressed air in Phase 2. Group 2 will receive the same agents in opposite order. Measures will be taken before and after the exposure. Experiments will be spaced at least 1 week apart.

- This is a prospective, double-blind, interventional, placebo controlled trial. Participants will be randomly allocated to Group 1 or Group 2. Group 1 will receive oxygen (99%) in Phase 1, and room air (placebo) in Phase 2. Group 2 will receive the agents in opposite order to Group 1. Measures of sensory function will be taken before and after each exposure. Two experimental days are planned for each phase, so that von Frey hairs and reflexes are tested on separate occasions to avoid cross-contamination. Both high oxygen and room air will be delivered through a loose fitting face mask approved by Health Canada (license #81363, supplied by Glenwood Labs, Canada, part # 1041). The flow rate will be 10 litre/min for a 2-min period.
- The participants with SCI will be blinded. The experiments will be spaced by at least 2 weeks.
- Primary outcome measure: skin sensation will be collected at regular intervals using calibrated Von Frey Hairs. Reflex and skin sensation will be recorded throughout the 30 min prior to and 30 min after exposure to high oxygen or room air at regular intervals. Secondary outcome measure: leg reflexes will be elicited by electrical stimulation of the skin, and responses measured by surface electromyography.
- The experimenter collecting the sensory data and the experimenter analyzing the reflex data will be blinded to the oxygen/air exposure, to avoid bias. The blinding ends for both the participant and the experimenter once the both experiments are completed for that participant.
- Stopping rules/discontinuation criteria: if any symptoms of early oxygen toxicity emerge, including acute tracheobronchitis, which could be a mild tickling sensation, later followed by inspirational pain, cough, or a constant retrosternal burning sensation (Klein 1990), the experiment will be stopped immediately. Normally, these types of symptoms are not

experienced until after 3 or more hours of exposure to high oxygen. If such an incident occurs with any participant, the study team will consider terminating the study.

Uninjured participants (n=10) will be included to test the study protocol for reflexes and von Frey hairs, but using compressed air only. This is to ensure the smooth running of experiments for the participants with spinal cord injury, and to provide reliability information on our testing procedures. Four experiments will be included to test the von Frey hairs and the reflexes in separate experiments, each repeated once to examine reliability of the testing (see Figure 2).

[figure not shown]

Figure 2. Experimental design for uninjured participants. Four experiments are planned for each participant. Only compressed air will be used in these experiments. Von Frey Hairs will be used to test sensation on 2 separate occasions, and reflexes will be used in the other 2 occasions.

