3.3 Randomization

The allocation of participants into Group 1 or Group 2 will be block randomized (block size 2-4) for each participant using a random sequence generator. Only one researcher present in the experiment will know the order of presentation for ease of administration and for safety, but all other experimenters doing the measurements and analyzing the data will be blinded.

Maintenance: the order of presentation can be disclosed to the participant and experimenters after all data has been collected on a participant.

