7.1 Statistical Methods

The data will be analyzed promptly, typically within a week of data collection. Statistical analysis will be done later after all data is collected and a statistician will be consulted to assist with analyses. The staff analyzing the reflex data off-line will be blinded.

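### Disclosing each participant's gas order as that participant finishes, with two orders in blocks of 2-4, helps testers guess later orders and can precede the reflex analysis.

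*Protocol*

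**What the plan says.** Two places in the Protocol say when blinding ends.

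- Section 3 (Trial Design): "The blinding ends for both the participant and the experimenter once the both experiments are completed for that participant".
- Section 3.3 (Randomization, under Maintenance): "the order of presentation can be disclosed to the participant and experimenters after all data has been collected on a participant".

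Both act participant by participant. Neither waits for the last participant or for the analysis.

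The Protocol also says who must be blinded. Section 3: "The experimenter collecting the sensory data and the experimenter analyzing the reflex data will be blinded to the oxygen/air exposure, to avoid bias". Section 3.3, after allowing one researcher to know the order: "all other experimenters doing the measurements and analyzing the data will be blinded". Section 7.1: "The staff analyzing the reflex data off-line will be blinded". On timing, section 7.1 adds: "The data will be analyzed promptly, typically within a week of data collection".

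On allocation, section 3.3 says participants "will be block randomized (block size 2-4) for each participant using a random sequence generator", and section 3 says "Group 2 will receive the agents in opposite order to Group 1". The Study Summary gives one centre and 25 participants with spinal cord injury. Sections 3.2, 3.5 and 4.4 give four sessions per participant, two with each gas.

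**The concern.** A permuted block must balance, so knowing the earlier orders in a block tells something about the next. With only two orders and blocks this small, it can tell a good deal. Because the second group's order is the exact reverse of the first's, a tester who guesses the order guesses the gas at every session of that participant. Nothing in the Protocol assigns different testers to later participants.

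The primary endpoint is skin sensation tested with von Frey hairs, which a tester applies. Section 3 gives avoidance of bias as the reason for blinding that tester. A tester who does better than chance puts the oxygen-minus-air contrast at risk of expectation bias.

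Two related defects sit in the same sentences. First, release of the order depends on finished experiments or collected data, not on finished analysis. Second, section 3 speaks of two experiments where the design has four sessions.

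**Working it through.** The Protocol gives no figure for predictability, so there is none to reproduce.

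**Inputs.** Two orders (section 3); blocks of 2-4 (section 3.3); 25 injured participants (Study Summary). Assumptions: 1:1 allocation, so that only block sizes 2 and 4 balance; the tester learns each order when it is released and guesses the order under-represented so far.

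**One full block, all earlier orders and the block start known.** The chance of a correct guess at each position is the larger number of places left for either order, divided by all places left.

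- Block of 2: 1/2 + 1 = 1.5 correct of 2, or 75%.
- Block of 4: 1/2 + 2/3 + (1/3 × 1 + 2/3 × 1/2) + 1 = 1/2 + 2/3 + 2/3 + 1 = 2.833 of 4, or 70.8%.

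**Twenty-five participants, run one after another.** The 25th participant starts a new block and adds 0.5.

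- All blocks of 2: 12 × 1.5 + 0.5 = 18.5 of 25, or 74%.
- All blocks of 4: 6 × 2.833 + 0.5 = 17.5 of 25, or 70%.
- Sizes 2 and 4 mixed 50:50 and unknown to the tester: 71% (about 17.8 of 25), from simulated allocation lists with a Bayesian predictor. The simple rule of guessing the under-represented order gives the same result without knowing block sizes.
- Three quarters of blocks of size 2, sizes unknown: 72%.
- No disclosure: 50%, or 12.5 of 25.

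**Orders known with certainty.** In the hidden mix, two like orders at the start of a block of 4 fix the next two. That makes about 2.6 of 25 orders certain (10%) when participants do not overlap. The figure runs from 1.6 to 3.4 as the share of blocks of 2 falls from 75% to 25%.

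**Overlap.** Correct-guess rate at a participant's first session:

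| Earlier participants still undisclosed | All blocks of 2 | All blocks of 4 | Hidden 2/4 mix |
|---|---|---|---|
| 0 | 74% | 70% | 71% |
| 1 | 50% | 58% | 55% |
| 2 | 50% | 54% | 53% |
| 3 | 50% | 50% | 50% |

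The rate rises again at later sessions of the same participant once those earlier orders are released.

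**How much overlap is likely.** The Protocol does not say. Its dates leave room for little: 25 participants × the 7-week minimum in section 3.5 = 175 weeks, against about 234 weeks from the amendment date (October 1, 2021) to the projected end (March 31, 2026). This does not show that participants run singly, since the actual start and pace are not given.

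**Reflex analysis.** Section 3.3 allows release once a participant's data are collected. Section 7.1 puts the processing of those data typically up to a week later. If the last session is a reflex session, its data can be analysed after release. Section 7.1 says the staff are blinded but does not hold the order back until they finish, and the sentence in section 3 that ends blinding directly follows the one naming the reflex analyst.

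**Two experiments or four.** Read literally, section 3 could end blinding before all four sessions are done. Section 3.3 requires all data first. The two must be reconciled.

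**The case against.** The strongest reply is that 71% is the extreme case. It needs each participant to finish all four sessions and be disclosed before the next one starts. With three earlier participants undisclosed, the first-session gain is nil; if all blocks are of size 2, one is enough. The certain orders also fall away: about 1.3 of 25 at first session with one undisclosed, none with two. This stands, and the fair range is 50% to 74%.

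The gain also needs the same tester to serve successive participants, to be told the orders and to keep count, and section 3.3 only permits disclosure. That too is fair, although section 3 states flatly that blinding ends and nothing in the Protocol prevents any of these conditions.

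The route to bias may be narrow. Participants learn only their own order, after their own data are complete, so their blinding is untouched. If the von Frey response is the participant's own report, which the Protocol does not specify, what remains is cueing or recording by the tester. Each participant receives both gases, so foreknowledge cannot unbalance who receives which. These points limit the harm but do not remove it.

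On the reflex data, three sections say the analyst is blinded, and the sentence ending blinding names one experimenter in the singular. It need not cover the analyst. This is an ambiguity to close, not a stated plan for unblinded analysis. The reference to two experiments may be carried over from a two-session design, since the Study Summary also speaks of two experimental days, and section 3.3 offers a workable reading.

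**Conclusion.** The concern holds and should be fixed. Following the plan as written weakens the blinding of testers and analysts that sections 3, 3.3 and 7.1 require. This is a stated rule, not a detail left for later.

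Under 1:1 allocation in blocks of 2 and 4, with testers who learn each released order, correct guesses range from 50% (heavy overlap, first session) to 70-74% (no overlap). The Protocol does not fix where in that range the trial will fall. The size of any resulting bias in the oxygen-minus-air contrast cannot be derived from it either. Confidence is high about what the text permits; actual harm is not shown. The reflex-analysis timing and the count of experiments are inconsistencies to reconcile.

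**What to change.** Replace the sentence in section 3 that ends blinding, and the Maintenance sentence in section 3.3, with one rule, for example:

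> The order of presentation will not be released to participants, to experimenters taking measurements or to staff analysing reflex data until the von Frey and reflex data of the last participant with spinal cord injury have been collected, analysed and locked, except for emergency unblinding. Only the single unblinded researcher described in section 3.3 holds the allocation list and the block sizes.

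This returns the expected correct-guess rate to 50% for any block size, ties release to completed analysis and removes the conflict over the number of experiments.

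The cost is protocol wording, and participants learn their order later, possibly by years given the projected end in March 2026. Withholding it only from testers and analysts would meet the risk identified, provided participants do not pass it on. The single rule is simpler and does not depend on that.

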3.1 Primary Study Endpoints/Secondary Endpoints

The primary endpoint is the skin sensation as quantified by von Frey Hairs at specific skin locations above and below the level of injury. The exact skin location will vary, since different participants will have different levels of injury. The secondary endpoint is the reflex excitability as measured by surface electromyography (EMG) in the leg muscles, and induced by electrical stimulation of the surface of the skin on the foot arch.

3.2 Study Design/Type

Prospective, double-blind, placebo controlled cross-over trial, with randomized order of presentation of high concentration of oxygen (99%) vs room air (placebo). All participants will be exposed twice to both conditions over the course of the 4 experiments, and measures will be taken before and after each exposure. See Figure 1 and Point 3 Study Design for details.

3.3 Randomization

The allocation of participants into Group 1 or Group 2 will be block randomized (block size 2-4) for each participant using a random sequence generator. Only one researcher present in the experiment will know the order of presentation for ease of administration and for safety, but all other experimenters doing the measurements and analyzing the data will be blinded.

Maintenance: the order of presentation can be disclosed to the participant and experimenters after all data has been collected on a participant.

